#### **3.2.3 Study Screening Questionnaire**

All volunteers attending who have attended and consented to the screening procedure will undertake a screening questionnaire with the assistance of the study doctor. This will outline medical history and inclusion and exclusion criteria for the study.

#### **3.2.4 Anthropometric measures**

In order to minimise variability in the measurements the same investigator will take all measurements. At the screening visit the following procedures for anthropometric measurement will take place

- **Weight measurement**

Study participants will have their weight measured on a digital equilibrated scale. The measurements will be taken between 10.00 and 11.00 after the volunteer has been asked to void. Volunteers will be weighted in their clothing with their shoes off and in barefeet or socks . Measurements will be recorded to the nearest 0.1Kg.

- **Height measurement**

Study participants will have their height measured using a stadiometer. This measurement will be taken in bare feet or socks. Patients will be asked to stand upright with their heels, buttocks and occiput touching the backboard of the stadiometer. The measuring arm of the stadiometer will be brought down to the top of the subjects head. Height is recorded to the nearest 0.1 cm.

- **Waist Circumference**

A non-stretch tape measure will be used to measure waist circumference. The measurement will be taken with the subject in a standing position with the abdomen relaxed, the arms at the sides and the feet together and breathing normally. The measurer faces the subject and places a measuring tape around the subject in a horizontal plane, at the mid-point between the lowest rib and the supra iliac crest. The measurement should be taken at the end of a normal expiration, ensuring the tape is taut around the subject's waist, without compressing the skin. Waist circumference measurements will be taken in duplicate and values will be recorded to the nearest 0.1cm. The mean value of both measurements will be recorded as the waist circumference.

### **3.2.5 Venepuncture**

At the study visits bloods will be taken to evaluate both fasting and post prandial gut peptide levels.

- A blood sample will be drawn approximately 10ml in total.
- They will be collected in the **fasting** state and **2 hours after meal initiation**.
- All samples will be acquired by a medical doctor with experience in phlebotomy.
  - 2x 5ml EDTA tube

Collected samples will be transferred to the laboratory and processed accordingly. Plasma samples will be centrifuged for 15 minutes at 2500g. The supernatant pipetted into aliquots. The aliquots will be labelled with the **subject recruitment number, visit number** and **“fasting”** or **“Post Prandial”**. Samples will be stored within a -20 freezer at the clinical research centre until processing of the samples commences. Waste will be disposed of in line with hospital waste disposal policies.

### ***3.2.6 Urinary pregnancy test***

Urine specimens will be collected on all women with child bearing potential prior to the administration of any drugs which the investigator and participant are blinded to. A spot urine sample will be collected from participants, transferred to the biochemistry lab and analysed for  $\beta$ HCG according to standardised method in the laboratory. Samples will be labelled with the volunteers name, date of birth and medical record number where available. Volunteers with an unexpected positive pregnancy will be informed by the investigator of the result, excluded from the study and referred to their primary care physician for further assessment.

### ***3.3 Randomisation***

For phase two, the randomised control trial. All subjects recruited will have been assigned an anonymised study number. Randomisation of volunteers to the intervention or placebo group will be undertaken using a web based randomisation programme. Subjects will be randomised to receive treatment A or B. Treatment A or B will correlate to either Octreotide 1 $\mu$ g/Kg or 0.01ml/Kg of 0.9% Saline. The buffet meal will be undertaken 60 minutes following the administration of either treatment A or B. At the subsequent study visit subjects will receive the opposite treatment in a crossover manner. The research investigator and volunteer will be blinded to the treatment. Unblinding will only take place at the end of the intervention study and data on all subjects has been statistically analysed.

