## ***2 Study Objectives and Design***

### ***2.1 Objectives***

The primary objectives of this study are

[figure not shown]
1. Determine the effect of Roux-en-Y gastric bypass (RYGB) surgery on food preference using a standardised Buffet meal.
2. Determine if the changes in food preference following RYGB are mediated through changes in gut peptide following surgery.

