### ***2.2 Design***

The Study will be conducted in two parts. The first phase of the study is an observational component where participants who are due to undergo RYGB surgery in addition to a matched control group will have their food preference assessed using a standardised macronutrient self selection paradigm (MSSP). This process will be undertaken 1 months pre and 3, 12 and 24 months post surgical intervention (See figure 1). The control group will be studied at matched time points. This will allow determination of the primary outcome, whether RYGB surgery alters food preference. Phase two of the trial will focus on understanding potential mechanisms responsible for altered food preference. It will take the form of a randomised control study whereby subjects following RYGB and controls will be

invited to repeat the MSSP after randomly receiving octreotide or saline placebo in a blinded crossover fashion. This assessment will take place one year following surgery.

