Each subject will have access to their own individual buffet table. Subjects will be asked to place any mobile electronic devices that they have brought with them into a sealed container in their room, with all electronic devices switched off. Reading material and media sources in the form of television or radio will be provided. Subjects will be instructed to alert the research team when they have finished eating, or should they experience any problems. After providing these instructions and answering any questions the subject may have, the investigator will then leave the room.

At this point a member of the research team will record the exact quantity of each foodstuff chosen by each subject by determining change in test food container weight.

At each of the 12 month visits, patients eligible for randomisation will receive a subcutaneous injection of either 1µg/kg octreotide(Sandostatin® 100microgram/ml) or 0.01ml/Kg 0.9% saline, in a random sequence. The study meal will be initiated directly after the completion of the baseline blood test on study visits not requiring a subcutaneous injection. Where subjects have received an injection of octreotide or saline, the meal will be initiated one hour after injection to ensure adequate serum concentrations of octreotide have been achieved.

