##### **Study Visit 3: Week 52**

1. Anthropometric Assessment: Height, weight, BMI and waist circumference
2. Fasting Gut peptide level
3. Randomisation to treatment A or B (Saline or Octreotide)
4. Administration of blinded Study drug prior to buffet meal
5. Buffet meal
6. Post prandial bloods
7. Urinary Pregnancy test

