## **9 Statistical analysis**

Data will be analysed using GraphPad Prism (version 6.0) for Windows, GraphPad software (San Diego, CA, USA) and SPSS® (version 20.0) software (SPSS, Chicago, IL, USA). Central tendencies for patient and control group demographics, anthropometric data, caloric intake and macronutrient intake will be calculated and expressed using arithmetic mean  $\pm$  standard error of the mean or median (range), as appropriate. Differences in continuous variables between surgical and control groups will be calculated using the Student's *t* test or Mann-Whitney U test for parametric or non-parametric data, respectively. Correlative analyses will be performed using the Spearman Rho rank correlation to assess the relationship between *ad libitum* caloric intake and macronutrient intake with peri-operative weight loss and anthropometric data. Univariate analysis of factors associated with perioperative and post-surgical weight loss will be performed using Student's *t* test or one-way ANOVA for categorical variables or simple logistic regression for continuous variables. For the multivariate analysis, independent variables which were significant on univariate analysis, including standard demographic, food intake and food preference, will be entered into a multiple logistic regression model with a forward stepwise selection procedure to assess their impact on perioperative and post-surgical weight loss. All statistical analyses will be two-tailed with the threshold of significance set at  $P < 0.05$ .

Although the patients will be tested at all of the time points. Sample size has been estimated based on Gregersen *et al.*[2] who suggest that 35 patients will be required per group in an unpaired study design to detect a 300kJ difference in overall caloric consumption between two groups with a power of 0.8. We anticipate that single-sitting food intake after upper GI surgery will be approximately 60-80% that of matched controls. Given a control *ad libitum* caloric intake of approximately 600kcal, this would equate to a 120 – 240kcal difference in caloric intake. In addition, differences in preferred food types will be studied.

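### The phase-two crossover has no planned within-subject, period-adjusted analysis, and the plan does not say whether treatment order is blocked or stratified by surgical group

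*Combined protocol and SAP*

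**What the plan says.** Phase two serves the second primary objective in section 2.1: "Determine if the changes in food preference following RYGB are mediated through changes in gut peptide following surgery". Section 2.2 puts both populations into it ("It will take the form of a randomised control study whereby subjects following RYGB and controls will be") and says that they are "invited to repeat the MSSP after randomly receiving octreotide or saline placebo in a blinded crossover fashion".

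On allocation, section 3.3 says "Randomisation of volunteers to the intervention or placebo group will be undertaken using a web based randomisation programme", and then "At the subsequent study visit subjects will receive the opposite treatment in a crossover manner". Section 3.5 describes the two injections as given "or 0.01ml/Kg 0.9% saline, in a random sequence". The list for Study Visit 3 in section 4 adds only "Randomisation to treatment A or B (Saline or Octreotide". None of these places gives an allocation ratio, a block structure, a stratification factor or the number of lists.

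Section 9 compares surgical and control groups with a Student's t test or Mann-Whitney U test, and adds correlations and regressions on weight loss. It has no octreotide-versus-saline comparison, no period or sequence term and no drug-by-group contrast. Its only sample size is for an unpaired comparison: "35 patients will be required per group in an unpaired study design to detect a 300kJ difference in overall caloric consumption". Phase two has no sample size of its own.

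**The concern.** Objective 2 needs an octreotide-saline difference that can be trusted in the RYGB group, and a comparison of that difference with the one in controls. In a two-period crossover, a paired mean that ignores period contains the drug effect plus the period effect multiplied by the sequence imbalance. If order is balanced within each group, that second term is close to zero. If it is not, part of any change between the first and second 12-month meals is counted as drug effect. The imbalance can also differ between RYGB and controls, so the contrast between groups can be shifted as well.

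There are two ordinary safeguards: balance the order by design within each group, or remove the period effect in the analysis. The plan states neither.

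**Working it through.** **Inputs from the documents.** 35 per group, 300 kJ, power 0.8, two-sided 0.05, control intake of about 600 kcal (all section 9).

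**Assumptions.** Simple 1:1 randomisation of order; 20 to 35 subjects per group in the crossover (section 9 gives 35 for phase one, and section 3.1.2 excludes some subjects from octreotide); a period effect of 60 kcal (10% of 600), with a range of 100 to 300 kJ; an SD of within-subject differences of 448 kJ.

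**1. The plan's own figure.** No SD is stated, so 35 per group cannot be reproduced directly. Solving for the SD: 300 / [√(2/35) × (1.960 + 0.842)] = 448 kJ. For comparison, an SD of 400 kJ gives 28 per group and 500 kJ gives 44. This is a surgery-versus-control calculation and does not size the crossover.

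**2. Chance imbalance within one group.** With X ~ Binomial(35, 0.5):
- P(22:13 or worse) = P(|2X − 35| ≥ 9) = 0.175
- P(23:12 or worse) = P(|2X − 35| ≥ 11) = 0.090
- P(at least one of the two groups at 22:13 or worse) = 1 − (1 − 0.175)² = 0.32

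With 20 per group, P(60:40 or worse) = 0.50 and P(65:35 or worse) = 0.26.

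**3. Share of the period effect that enters.** The unadjusted paired mean equals drug effect + period effect × (difference in sequence sizes)/n.
- At 22:13: 9/35 = 0.257, or 26%.
- SD of this fraction: 1/√35 = 0.169 for one group, and √(2/35) = 0.239 for the RYGB-control contrast.
- Mean absolute fraction at n = 35: 0.14; 95th percentile: 0.31.

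**4. Size of the leak.**
- 60 kcal × 9/35 = 15.4 kcal (64.5 kJ) at 22:13.
- For period effects of 100 to 300 kJ: 26 to 77 kJ at 22:13, and 37 to 111 kJ at 24:11.
- The standard error of the paired mean is 448/√35 = 76 kJ (18 kcal), so the 64.5 kJ leak is 64.5/76 = 0.85 of a standard error.

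**5. Type I error (simulation, n = 35, SD 448 kJ).**

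| Setting | Period effect 150 kJ | Period effect 300 kJ |
|---|---|---|
| Unadjusted, averaged over simple randomisation | 0.052 | 0.050 |
| Unadjusted, given 21:14 | 0.054 | 0.061 |
| Unadjusted, given 24:11 | 0.093 | 0.189 |
| Unadjusted, order held at 18:17 | 0.038 | 0.019 |
| Period-adjusted, simple randomisation | 0.051 | 0.051 |
| Period-adjusted, order held at 18:17 | 0.049 | 0.049 |

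The fourth row shows that balance alone is not enough. Without a period term, the period effect inflates the residual spread and the paired test becomes conservative.

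**6. Cost of adjusting for period.** The variance relative to a balanced split is (1/a + 1/b)/(4/35): 1.04 at 21:14, 1.07 at 22:13 and 1.16 at 24:11.

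**7. Effect of blocking.** Blocks of 4 within each group hold the sequence difference to at most 2 subjects. With 35 subjects and an 18:17 split, the leak is 1/35 = 3% of the period effect.

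**The case against.** The plan is silent on the list method, and silence is not a choice of simple randomisation. A reader might infer that RYGB subjects and controls are drawn from one unrestricted list. No section says so, and a web programme may well block and stratify. A reader might also take section 3.3's wording about an intervention or placebo group to mean a parallel allocation. The rest of that section, together with section 3.5, makes clear that order is what is randomised. Both of these objections stand.

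A visit-order effect is also not shown to be likely. Visits 3 and 4 are both labelled week 52, but no interval is given. By the visit lists in section 4, subjects have already met the buffet at weeks −4 and 12, and section 3.5 re-randomises food order at each visit. This objection stands too: the period effect is an assumption.

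Simple randomisation gives no bias on average, and every subject receives both treatments, so imbalance of order does not confound subject characteristics with drug. The 15 kcal leak is small beside the 120 to 240 kcal that section 9 expects between surgery and control, although that is a phase-one benchmark and none exists for octreotide.

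None of this supplies the missing analysis. Whatever the programme does, section 9 contains no paired comparison and no period term.

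**Conclusion.** The point holds as a modest one with two parts. The more important is that section 9 gives no within-subject analysis of the crossover. The lesser is that section 3.3 does not say how order is balanced within each surgical group.

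Harm requires three things together: a chance imbalance of order, a real period effect, and an analysis that ignores period. Under simple 1:1 randomisation with 35 per group, a 22:13 or worse split has probability about 0.18 in a given group. At 22:13, 26% of the period effect enters the unadjusted estimate, about 15 kcal if that effect is 60 kcal. The group size, the allocation method and the period effect are all assumptions. Fewer subjects in phase two would make imbalance more likely.

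The documents do not support the stronger reading that the octreotide estimate will be biased. Averaged over randomisations the type I error stays near 0.05, and inflation appears only conditional on an uneven split.

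**What to change.** **First, section 9.** Analyse octreotide versus saline within subject, with terms for treatment, period, sequence, surgical group and treatment-by-group. Allow the period effect to differ between RYGB and controls, since a common period term would not fully remove group-specific visit effects. The cost is about 7% in variance at 22:13 and almost nothing near balance. This can be specified at any time before unblinding.

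**Second, section 3.3.** State that subjects are randomised 1:1 to sequence (octreotide then saline, or saline then octreotide) in permuted blocks of varying size, separately for RYGB and controls. This is a setting in the web programme and one sentence of text, with no added subjects or visits, but it must be in place before the first subject is randomised. The downside is slight predictability within a block, which varying block size and blinding limit. If the programme already does this, only the sentence is needed.

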### ***3.4 Study Drug preparation and administration***

#### **Octreotide (Sandostatin® 100 $\mu$ g/ml, Novartis Ireland)**

- The drug will be stored in line with manufacturer instructions.
- As the study drug will be blinded to the research investigator, the research nurse will be charged with preparing the study drug.
- A dose of 1 $\mu$ g/Kg will be drawn up by the research nurse and labeled with the appropriate code **Treatment A** or **Treatment B**.

- The weight used will have been recorded prior to drug administration
- This drug will be administered using a sterile technique to the participant's subcutaneous tissue.
- It will be given 60 minutes prior to the Buffet meal.
- A menstrual history and urinary pregnancy test will be completed on all females of child bearing potential prior to the administration of any drug.

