## **5 Adverse event program**

### **5.1 Subject premature Withdrawal**

If a study volunteer fails to complete the study protocol it will be documented in the individual case report form. The reason for failure to complete the study will be included in the CRF. Study Subjects may be withdrawn for the following reasons

- Adverse Event(s) (AEs)
- Abnormal laboratory value(s)
- Protocol violation
- Subject withdrew consent
- Lost to follow-up
- Death

All patients who withdraw early from the study will have their GP informed in writing that their participation in the study is complete. In the event of adverse event, GP's will be informed and arrangements will be made for subjects who have a requirement for ongoing medical follow-up as a consequence of an adverse event.

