### **5.2 Adverse Events (In accordance with the ICH)**

An adverse event (AE) is defined as “any untoward medical occurrence in a patient or clinical investigation subject administered a pharmaceutical product and which does not necessarily have to have a causal relationship with this treatment”. The principal investigator (PI) will be informed of any adverse events affecting participants within 24 hours of the research investigator becoming aware of them. The suitability of the participant to continue with the study will be determined by the PI. All adverse events will be recorded in the CRF and the adverse events log contained within the site file. A data safety monitoring committee will be established consisting of senior physicians. All events will be reported within 7 working days and decisions to progress or stop the study will be made in conjunction with the Ethics committee.

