### **5.3 Serious Adverse Events**

A serious adverse event (SAE) or reaction is defined as any untoward medical occurrence that:

- results in death
- is life-threatening
- requires inpatient hospitalisation or prolongation of existing hospitalisation
- results in persistent or significant disability/incapacity, or
- is a congenital anomaly/birth defect.

The term "life-threatening" in the definition of "serious" refers to an event in which the patient was at risk of death at the time of the event; it does not refer to an event which hypothetically might have caused death if it were more severe. The principal investigator (PI) will be informed of any adverse events affecting participants within 24 hours of the research investigator becoming aware of them. The suitability of the participant to continue with the study will be determined by the PI. All adverse events will be recorded in the CRF and the adverse events log contained within the site file. A data safety monitoring committee will be established consisting of senior physicians. All events will be reported within 7 working days and decisions to progress or stop the study will be made in conjunction with the Ethics committee.

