## ***11 Administrative considerations***

### ***11.1 Changes to the conduct of the study/Amendments to study protocol***

Any and all amendments to the protocol must be agreed upon by the named investigators of the study. All protocol amendments must be submitted to the institutional ethics committee for approval. Informed consent documents must be updated with amendments appropriately and submitted with application for protocol revision. Changes to the protocol may not be implemented prior to ethical approval unless it is intended to eliminate an immediate hazard to the study subject. In this case study sponsor and ethics committee must be informed as soon as possible of the deviation.

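### Section 3.3 bars unblinding until the intervention study is finished and analysed, and no section makes an exception for an individual participant's safety

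*Combined protocol and SAP*

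**What the plan says.** All references are to the combined protocol and SAP.

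- **Blinding and unblinding (3.3).** The research investigator and the volunteer are the two parties named as blinded. The rule on lifting the blind is: "Unblinding will only take place at the end of the intervention study and data on all subjects has been statistically analysed". No exception follows.
- **Timing and design (2.2, 3.3).** The octreotide–saline crossover is phase two. Of its timing, 2.2 says: "This assessment will take place one year following surgery". Each participant receives one treatment at one visit and the other at the next.
- **Drug preparation (3.4).** Because the research investigator is blinded, "the research nurse will be charged with preparing the study drug". The nurse labels each dose A or B. No duty or permission to disclose is given.
- **Octreotide exclusions (3.1.2).** Liver disease, pancreatitis, bradyarrhythmia and seriously interacting medication are listed as exclusions from octreotide specifically.
- **Adverse events (5.1 to 5.3).** The PI is told within 24 hours. Then "The suitability of the participant to continue with the study will be determined by the PI" and "All events will be reported within 7 working days". A safety committee of senior physicians is to be set up. After an adverse event the GP is informed and "arrangements will be made for subjects who have a requirement for ongoing medical follow-up as a consequence of an adverse event".
- **Changes to conduct (11.1).** Changes need ethical approval first, "unless it is intended to eliminate an immediate hazard to the study subject".

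**The concern.** A blinded drug trial normally has a written route by which one participant's treatment can be disclosed when that person's care depends on it. Here the only rule on the subject is worded exclusively and tied to a study-level milestone.

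Suppose a participant develops pancreatitis or a bradyarrhythmia after a blinded injection. The protocol identifies both as reasons not to give octreotide. Whether the injection was octreotide or saline then bears on how the event is managed, what follow-up is arranged and what the GP is told. Staff who follow 3.3 to the letter would withhold that information. Staff who disclose it would be improvising, with no named person to ask and no record required.

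**Working it through.** No arithmetic applies. The check is whether any section supplies the exception that 3.3 lacks, and what is left uncovered if none does.

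1. **Is 3.3 the only rule?** Yes. The places where an exception would be expected are 3.2.6 (pregnancy test), 3.4 (drug preparation), 5.1 to 5.3 (withdrawal and adverse events) and 11.1 to 11.2 (changes and termination). None describes releasing an individual's treatment.

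2. **Does the adverse event section supply a route by implication?** No. Sections 5.1 to 5.3 say who is told and how quickly, and that follow-up is arranged. They do not say that the treatment may be revealed to any of these people.

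3. **Does 11.1 supply it?** In part. It allows the team to depart from the protocol before approval in order to remove an immediate hazard. That could justify an urgent code break. It does not name who holds the code or how to obtain it, and it does not clearly reach a serious event whose acute phase has passed but whose follow-up is still being planned.

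4. **Does anyone on site know the treatment?** Probably. Under 3.4 the research nurse draws up either octreotide or saline. Knowledge without stated permission does not settle the matter, because 3.3 on its face tells the nurse not to disclose.

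5. **What would the code add?** After the first phase-two visit only, it says whether the participant has been exposed to octreotide at all. After both visits exposure is certain, because of the crossover, and the code says which injection preceded the event.

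6. **What does not depend on the code?** Stopping further injections. The PI can withdraw a participant under 5.1 to 5.3 without knowing the treatment. What remains affected is acute care, follow-up and the information passed to the GP.

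**The case against.** The strongest reply has four parts.

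- **3.3 may be only a study-level rule.** The sentence sits under Randomisation and is tied to completion of the analysis, so it may mean only the release of the whole code. That reading is reasonable. The word *only* nevertheless makes the literal reading available, and nothing elsewhere corrects it.
- **Few people are declared blind.** 3.3 names the research investigator and the volunteer. Section 5.2 treats the PI as a separate role, and the blinding status of the PI and the safety committee is not stated. This stands: the documents do not show that these people are blinded, only that no route to the information is given.
- **Urgent cases are largely covered by 11.1.** This stands for immediate hazards only.
- **A clinician could simply assume octreotide was given.** That is often a safe working assumption, and the protocol names no treatment step that would change. It still leaves the follow-up plan and the GP letter resting on a guess when the fact is available.

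Three stronger readings are tempting and not supported.

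- A reader might infer that the PI must judge, blind, whether an event was caused by the drug. Sections 5.1 to 5.3 ask for no causality judgement.
- A reader might use the planned 36-month duration to work out how long participants would wait for the code and compare that with the 7-working-day limit. The interval between the two Week 52 visits and the analysis time are not given, and the limit concerns reporting an event, not knowing the treatment.
- A reader might make pregnancy the leading case. Section 3.2.6 says: "Volunteers with an unexpected positive pregnancy will be informed by the investigator of the result, excluded from the study". The code would matter only if a participant tested negative before the first injection and positive before the second. That is narrow.

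**Conclusion.** The concern holds in limited form. Section 3.3 states an exclusive rule, no section supplies an exception for an individual's safety, and following the rule literally gives a worse result for a participant with a serious event than a rule with an exception would. 11.1 covers only immediate hazards.

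The consequence is confined to acute care, follow-up and what the GP is told. Its frequency cannot be estimated, because no event rates are given. The analysis, sample size and error rates are unaffected. This is a cheap improvement to participant safety, not a defect in the inference.

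The conclusion rests on the literal reading of 3.3 and on the supplied text. Pages removed before review could not be checked for a code holder or an emergency contact procedure.

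**What to change.** Amend 3.3 to the following effect:

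*Unblinding takes place after the intervention study has ended and its data have been analysed, except that a designated unblinded code holder (for example the research nurse) may release a single participant's treatment to the PI, the treating clinician or the safety committee when this is needed for that participant's safety.*

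Add that each release is logged, and that the research investigator and those who assess the meal stay blind where possible. Cross-refer to this from 5.2 and 5.3. State at the same time whether the PI and the safety committee are blinded.

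**Cost.** One sentence in 3.3, two cross-references and an amendment to the ethics committee. Visits, sample size and analysis do not change.

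**Downside.** In a crossover, one release reveals both periods for that participant. If the labels A and B mean the same treatment for everyone, which the protocol does not state, a careless release could also expose the code for others. That is a further reason to name the holder and restrict who receives the information.
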